## Protocol

### Summary

One in three adults in the United States suffers from obesity. Bariatric surgery is an increasingly utilized and effective treatment for obesity and obesity-related comorbidities, however, the massive weight loss associated with bariatric surgery adversely affects bone metabolism. Significant decreases in bone mineral density lead to an increased risk of fracture and subsequent reduction in physical function among bariatric surgery patients. Bisphosphonate medications, such as zoledronic acid, have been evaluated for safety and efficacy in combating bone loss in patients with osteoporosis, but their use in bariatric surgery induced bone loss has not been explored. The study's primary goal is to investigate whether bisphosphonate therapies are able to combat bone loss associated with surgical weight loss procedures. This research proposal is a 1-year, pilot randomized controlled trial involving 20 adult sleeve gastrectomy participants randomized to receive either a onetime zoledronic acid infusion or placebo. The hypothesis is that zoledronic acid, a standard treatment for low bone density, will be an effective intervention to reduce sleeve gastrectomy-induced bone loss. Bone loss is an unintended consequence of an otherwise life-saving procedure, with declining bone health potentially contributing to major morbidity in those undergoing a bariatric procedure. Identifying effective interventions to minimize bone loss is crucial for comprehensive treatment of patients who undergo bariatric surgery. Specific Aim 1: To determine the efficacy of zoledronic acid in preventing bone loss associated with sleeve gastrectomy. We will measure bone mineral density and bone turnover markers at baseline and 9 months. The primary outcome is change in bone mineral density as measured by Dual-energy x-ray absorptiometry. Secondary outcomes are change in bone mineral density as measured by Quantitative Computed Tomography and change in the serum bone turnover markers, urinary collagen type 1 cross-linked N-telopeptide (a bone formation marker), serum type 1 procollagen N-terminal (bone resorption marker), sclerostin, and osteocalcin. Specific Aim 2: To evaluate the feasibility of this trial in those who have undergone sleeve gastrectomy surgery. We will assess the feasibility of the intervention by documenting adverse events and compliance rates at each study time point.

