## Statistical Analysis

In this pilot study, thirty participants will be enrolled: 15 randomized to the intervention group, and 15 randomized to the control group with a goal of 10 participants completing the study in each group. Data gathered from this study will be used to complete sample size and power calculations for a larger randomized controlled trial. A sample size of 10 per group achieves 80% power to detect a difference of -0.02 (correlation coefficient) between the null hypothesis correlation of 0.0 and the alternative hypothesis correlation of 0.02 using a two-sided hypothesis test with an estimated standard deviation of 0.02 and with a significance level of 0.05 using a two-sided Wilcoxon test, assuming that the actual distribution is normal.

Collection of study data is focused on feasibility and gathering evidence to inform future studies, thus, all analyses are considered exploratory rather than confirmatory. Baseline characteristics will be summarized using descriptive measures, both overall, by gender, and by group, at baseline. The primary outcome of feasibility will be based on retention of participants at follow-up visits and description of tolerance of the active and inactive group in response to infusion. Follow-up treatment effect estimates at 9 months will be used in power calculations for future clinical trials. Secondary analyses will examine change in bone metrics between groups assessed by a Students t-test. The effect of changes in relevant co-variates such as lean mass, muscle function and nutrition status on study outcomes will be assessed. Regression models will be used to control for appropriate co-variates and further explore the effect of zoledronic acid on bone after bariatric surgery.

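### The Summary randomises 20 participants and the Statistical Analysis randomises 30; separately, the stated 80% power is not reached at the plan's own 10 per group

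*Combined protocol and SAP*

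**What the plan says.** The Summary describes a one-year pilot trial "involving 20 adult sleeve gastrectomy participants randomized to receive either a onetime zoledronic acid infusion or placebo". It gives no completer target and no allowance for loss.

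The Statistical Analysis section says "thirty participants will be enrolled: 15 randomized to the intervention group, and 15 randomized to the control group". Its completion target is worded "with a goal of 10 participants completing the study in each group". No dropout rate is stated.

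The same section gives the power statement, which begins "A sample size of 10 per group achieves 80% power to detect a difference of -0.02 (correlation coefficient". The spread is given as "using a two-sided hypothesis test with an estimated standard deviation of 0.02". The level and the sizing test are then named: "with a significance level of 0.05 using a two-sided Wilcoxon test, assuming that the actual distribution is normal". The planned between-group comparison uses a different test: "Secondary analyses will examine change in bone metrics between groups assessed by a Students t-test". The section bases its primary feasibility outcome on retention at follow-up and tolerance of the infusion, and adds that "all analyses are considered exploratory rather than confirmatory".

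**The concern.** Both sentences give the number randomised in the same trial, and they differ by 10. Neither is superseded text.

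This number is the recruitment target and the denominator for retention, which the Statistical Analysis makes part of its primary outcome. If 20 people complete, retention is 67% of 30 but 100% of 20. Someone working from the Summary alone would stop recruiting at 20 and leave no room for loss, although the Statistical Analysis plainly expects some.

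The second question is whether 10 per group, the number to which the 80% is tied, delivers that power. The pilot is meant to inform the sample size of a larger trial, so an optimistic power statement could carry over into that design.

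**Working it through.** **Inputs.** All are from the Statistical Analysis except the first.
- Randomised: 20 (Summary) or 30, as 15 + 15 (Statistical Analysis).
- Completer goal: 10 per arm.
- Difference 0.02 in absolute value, SD 0.02, two-sided 0.05, normal data.

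The plan labels the difference a correlation coefficient. I assume that a difference in mean change in a bone measure is meant and that 0.02 is the SD of that change. The standardised difference is then d = 0.02 / 0.02 = 1.

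**Step 1: the plan's own 80% at 10 per group.** For a two-group t-test, the noncentrality is λ = d × √(n1·n2 / (n1 + n2)), and power is the probability that a noncentral t on n1 + n2 − 2 degrees of freedom falls outside ± the 0.975 critical value.
- t-test: λ = √(100/20) = 2.236, 18 df, critical value 2.101; power 56.2%.
- Normal approximation: Φ(2.236 − 1.960) = Φ(0.276) = 60.9%.
- Exact Wilcoxon rank-sum, 20,000 simulated trials: 51.4%.
- One-sided 0.05: 69.4% (t) or 72.3% (normal).

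None of these is close to 80%. A one-sample or paired t-test with n = 10 is: λ = √10 = 3.162 on 9 df gives 80.3%, and the signed-rank test gives about 79%. On the stated inputs, the 80% therefore matches a one-sample or paired calculation, not a comparison of two groups of 10.

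For 80% in a two-group comparison, about 17 completers per arm are needed by t-test (16.7 before rounding) and about 18 by Wilcoxon (16.7 × π/3 = 17.5). Even if all 15 per arm completed, t-test power would be 75.3%.

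**Step 2: what the two headcounts imply.** Going from 15 to 10 per arm implies retention of 10/15 = 67%, and 30 × 2/3 = 20 agrees with the completer goal. With 20 randomised, 10 per arm would need 20/20 = 100% retention. At 67%, 20 × 2/3 = 13.3 would complete.

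**Step 3: power if 20 were randomised.** Retention is an assumption here, so I show a range. Two-sided t-test, d = 1:

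| Assumed retention | Completers | λ | df | Power |
|---|---|---|---|---|
| 67% | 13 (7 and 6) | √(42/13) = 1.797 | 11 | 37.5% |
| 80% | 16 (8 and 8) | √(64/16) = 2.000 | 14 | 46.1% |
| 90% | 18 (9 and 9) | √(81/18) = 2.121 | 16 | 51.3% |
| 100% | 20 (10 and 10) | √(100/20) = 2.236 | 18 | 56.2% |

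By exact rank-sum, 6 to 7 per arm gives about 30% to 34%.

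**Step 4: retention precision.** Exact 95% intervals are 47% to 83% for 20/30 and 41% to 85% for 13/20.

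**The case against.** **A labelling slip.** The Statistical Analysis is the detailed design text: it gives the total, the split and the completer goal. The Summary's 20 equals 10 + 10 completers, so this is probably a slip of label. That is the likeliest explanation, and it keeps the correction small. It does not remove the conflict, because the Summary says randomised and never mentions completion.

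**Limited consequences.** This is a pilot whose analyses are all called exploratory, so power carries less weight than in a confirmatory trial. The retention intervals in Step 4 are wide either way and would be read much alike. Both points stand. What remains is that a protocol needs one recruitment target and one denominator, and that a power figure, once given, should be right.

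**Another reading of the SD.** If 0.02 were the SD of a single measurement, the SD of change would be 0.02 × √(2(1 − r)), where r is the correlation between baseline and follow-up. Two-group t-test power at 10 per arm would then be 32% at r = 0, 56% at r = 0.5 and 85% at r = 0.75. Since 80% needs d = 1.325, it would be reached at r = 1 − 1/(2 × 1.325²) ≈ 0.72. The plan states no such correlation, so this cannot support the 80% as written.

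**A stronger reading to avoid.** A reader might infer that following the Summary is what drops the trial from 80% power to under 40%. The documents do not support that. The power statement rests on 10 per group, and that number misses 80% even when 30 are randomised. At 67% retention, the Summary's number would account for a fall from about 56% to 38% by t-test, or from 51% to about 30–34% by rank-sum. Nor does the plan state a one-third loss: that rate is inferred from 15 to 10, so 13 completers is one scenario among several.

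**Conclusion.** The conflict is real: 20 against 30 randomised in current text, with 20 most likely the completer goal under the wrong label. Recruiting only 20 would make 10 completers per arm unreachable unless nobody were lost. That conclusion needs no assumed dropout rate. Two-group t-test power would be about 38% to 56% across retention of 67% to 100%.

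The 80% is a separate defect and does not come from the headcount conflict. At 10 per group, power is about 56% by t-test and 51% by the stated Wilcoxon test. These figures assume a two-group comparison, d = 1 on the plan's own inputs, and 0.02 as the SD of change. The exploratory status of the analyses limits the practical harm but does not make either statement correct.

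**What to change.** - **Summary:** state that 30 participants are randomised, 15 per arm, with a goal of 20 completing, 10 per arm.
- **Retention outcome:** name the 30 randomised as the denominator.
- **Power statement in the Statistical Analysis:** replace 80% with about 51% (two-sided Wilcoxon) or about 56% (t-test) for 10 completers per arm, and name the test used, preferably the one planned for the analysis. Drop the correlation wording and say what the SD of 0.02 refers to. If a correlation between baseline and follow-up was assumed, state its value and recompute.

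The cost is one sentence in the Summary and small edits to the Statistical Analysis. No patients are needed beyond the 30 already planned. The only downside is a less favourable stated power, which a pilot with exploratory analyses can accept.

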### Purpose

The purpose of this study is to evaluate the effect of zoledronic acid, a bisphosphonate medicine used for osteoporosis, in preventing bone loss after bariatric surgery.

Specific Aim 1: determine the efficacy of zoledronic acid in preventing bone loss associated with sleeve gastrectomy (SG).

Specific Aim 2: evaluate the safety and tolerance of zoledronic acid in populations who have undergone SG surgery.

### Background

Bone loss is accelerated after sleeve gastrectomy (SG) procedures, which can lead to an increased incidence of fragility fractures. This problem is becoming increasingly more important as bariatric surgery rates continue to rise. Fragility fractures due to poor bone health, are a leading cause of morbidity in older adults. Observational studies link weight loss with a reduction in bone mineral density (BMD) and an increased fracture risk, regardless of initial body weight. Dietary-induced weight loss

interventions have also been associated with decreases in total hip BMD. Greater weight loss exacerbates this decline in BMD and subsequent risk of fracture. (Tirosh, 2015) Data collected in the year following bariatric surgery shows a rapid decline in BMD and a significant association between bariatric surgery and fracture risk. Emerging long-term data suggest that bone loss continues in these patients even after weight stabilizes, with elevated bone turnover markers seen up to five years post-surgical treatment and fracture risk remaining high in long-term follow up. While cardiovascular and metabolic health improve after bariatric surgery, patients are increasingly vulnerable to fracture and the associated disability and morbidity. Bariatric surgery irreversibly increases skeletal fragility and future fracture risk. Identifying effective interventions to minimize bone loss is crucial for comprehensive treatment of patients who undergo bariatric surgery. There are many available pharmacotherapeutic options to effectively treat low bone density and decrease fracture risk. These treatments include anti-resorptive agents, such as the bisphosphonate zoledronic acid, which inhibit osteoclast-mediated bone loss. Bisphosphonates have been well studied for safety and efficacy in the treatment of low bone density in non-surgical populations, but the question of whether these pharmacotherapies may benefit patients after surgical weight loss procedures still remains. Guidelines put forth by The American Association of Clinical Endocrinologists sparsely address bisphosphonate use after surgical weight loss, and further evidence is needed to provide robust recommendations for prevention of bone loss after bariatric procedures. Weight loss is associated with a significant increase in bone resorption which is mediated by osteoclasts. This makes bisphosphonates an appropriate treatment choice. Thus, bisphosphonate use may prove to be an effective intervention for countering bone loss during active weight loss, which is critical in reducing long-term fracture risk in the bariatric surgery population.

Bariatric surgery has resulted in remarkable cardiovascular and metabolic health improvements, but often this occurs at the expense of bone health. The full extent of the lifelong consequences of bone loss on quality of life and mobility are not known. This study is significant because it could provide evidence for use of an existing therapy to counteract bone loss seen in post-bariatric surgery patients.

## Methods

Enrolled participants will have blood drawn from the to evaluate menopausal status in those < 60 years old. Study personnel will also collect and store serum at 80 degrees Celsius, for assay of bone turnover markers and metabolic regulator proteins at a later date. Analysis of bone formation markers including procollagen Type 1 N-TerminalPropeptide (P1NP) and bone resorption marker N-Terminal Telopeptide of Type 1 Collagen (CTX) will be performed via commercially available ELISA by our laboratory. Participants will complete three surveys at baseline. The first, the Human Activity Profile (HAP), is a 94-question physical activity survey used to assess routine physical activity. The second, the Knee Injury and Osteoarthritis Outcome Score (KOOS), will assess overall knee pain, function, and knee-associated problems. Participants will also complete a modified National Osteoporosis Foundation Calcium Intake Estimate to collect dietary calcium habits. Participants will then be asked to perform three tasks relating to muscle function and gait speed: hand grip test, repeated chair stands, and a four-meter gait speed test. Participants will be measured on a standard scale for weight and have their waist circumference measured by study personnel.

Participants will obtain dual energy x-ray absorptiometry (DXA) scan or bone densitometry scan and a computed tomography (CT) scan at baseline. Bone density measurement (BDM) of the bilateral hips, spine, radius, proximal tibia as well as body composition will be measured by DXA. A CT scan of the spine and hip will be completed using the Mindway Phantom to assess bone density and bone structure, as

well as abdominal composition. CT scans will be de-identified and transferred to Wake Forest University to complete analyses of the CT scans.

All participants will receive calcium citrate and vitamin D supplements, with instructions for taking. Calcium, Vitamin D, and Bariatric ProCare multivitamins will be processed and dispensed by the research pharmacist. A total intake of 1200 mg of calcium will be prescribed throughout the entirety of the study. Participants with normal serum 25(OH)D will be prescribed 1000 IU Vitamin D. Participants with serum 25(OH)D between 20-29mg/mL will be prescribed 2000 IU Vitamin D. Vitamin D will be prescribed for the pre-operative period. Following non-study surgery, participants will be instructed to take the Bariatric ProCare vitamins and calcium citrate, and to discontinue any remaining Vitamin D supplements.

Participants will be contacted via email and phone as a reminder prior to their infusion date. They will be provided with an appointment reminder text and directions to the Clinical Research Center with instructions on what to expect at their study visit. Based on prior randomization, participants will receive either non-active saline (placebo) or active-medication (zoledronic acid) infusion. To minimize the risk of adverse effects of Zoledronic acid, all participants will have a baseline glomerular filtration rate (GFR) measured prior to infusion to ensure they have adequate kidney function. A stat blood draw with comprehensive metabolic panel will be ordered prior to the infusion. Those participants with glomerular filtration rate (GFR) less than 35mL/min or those with evidence of acute kidney impairment will not receive the treatment. A single dose of Zoledronic acid should not exceed 5mg, and the duration of infusion should be no less than 15 minutes. Therefore, infusion of both the active and non-active intervention will take place over 15 minutes. To minimize risk of adverse events such as anaphylaxis, a Clinical Research Center nurse will be present during the infusion and will monitor the patient for 15 minutes after the infusion. Adverse events including potential infusion reaction and other side effects will be recorded by study personnel at the time of infusion. Participants will be provided with a take-home sheet detailing common and/or expected reactions to the medication intervention, with instructions as to how to manage them. This sheet will be reviewed with the participant by study personnel, with ample time for questions.

Participants will be contacted via text message, email or phone call 24-hours and 2-months following their infusion to collect and address any adverse events/reactions/concerns they may have. The contact will include a link to a RedCap survey to self-report adverse events. If contacted via phone, study personnel will complete the adverse events form with the participant. Participants will be contacted up to 3 times, with at least 24 hours between contact in the case of non-responders.

Nine months post-bariatric surgery, participants will have a follow-up visit. Participants will be measured on a standard scale for weight and have their waist circumference measured. Participants will have blood drawn and serum will be stored at 80 degrees Celsius, for assay of bone turnover markers and metabolic regulator proteins at a later date. Analysis of bone formation markers including procollagen Type 1 N-TerminalPropeptide(P1NP) and bone resorption marker N-Terminal Telopeptide of Type 1 Collagen (CTX) will be performed via commercially available ELISA by our laboratory. Participants will complete three surveys: the Human Activity Profile (HAP), is a 94-question physical activity survey used to assess routine physical activity; the Knee Injury and Osteoarthritis Outcome Score (KOOS), will assess overall knee pain, function, and knee-associated problems; and a modified National Osteoporosis Foundation Calcium Intake Estimate to collect dietary calcium habits. Participants will complete a hand grip test, repeated chair stands, and a 4-meter gait speed test. The National Osteoporosis Foundation Calcium Intake Estimate will be used post-operatively to gather data about calcium intake from diet.

A whole body DXA scan will be obtained one month after follow-up visit to assess body composition and bone mineral density (BMD) of the hip, lumbar vertebrae (L1-L4), knee and radius. To minimize variability between baseline and follow-up scans, each participant will be scanned on the exact same DXA scanner with identical scan parameters for each anatomic location. A real BMD (a BMD, g/cm^2) will be determined from each scan. For the femoral scan, a BMD will be calculated from the proximal femur using the scanners standard procedures. For the vertebral scan, a BMD will be calculated for each vertebral body and for all four combined using the scanners standard procedures. For the distal radius scan, a BMD will be calculated for the distal one-third of the radius using the scanners standard procedures. The DXA technologist will be blinded to treatment group for each subject. The whole body DXA also provides data on lean and fat mass, as well as distribution of these tissues. A CT scan of the lumbar vertebrae, hips and associated soft tissue will be obtained from one month after follow-up visit. To minimize variability between the baseline and follow-up scans, each participant will be scanned on the exact same CT scanner with identical scan parameters.

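### Allocation is fixed before the kidney check that decides who is infused; releasing it after the result would avoid most randomised but uninfused participants

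*Combined protocol and SAP*

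**What the plan says.** The protocol's Methods section describes the infusion visit in this order:

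- Allocation already exists: "Based on prior randomization, participants will receive either non-active saline (placebo) or active-medication (zoledronic acid) infusion".
- Kidney function is then checked in everyone: "all participants will have a baseline glomerular filtration rate (GFR) measured prior to infusion to ensure they have adequate kidney function".
- A rapid panel is tied to the visit: "A stat blood draw with comprehensive metabolic panel will be ordered prior to the infusion".
- The result can stop the infusion: "Those participants with glomerular filtration rate (GFR) less than 35mL/min or those with evidence of acute kidney impairment will not receive the treatment".

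Statistical Analysis gives the numbers as "15 randomized to the intervention group, and 15 randomized to the control group", "with a goal of 10 participants completing the study in each group". It compares bone changes between groups with a t-test, names feasibility (retention and tolerance) as primary, calls all analyses exploratory, and intends to use the 9-month effect estimates to power a later trial.

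Neither section says whether a person who is randomised but not infused is followed, replaced, kept in the assigned group or left out. The adverse-event contacts at 24 hours and 2 months are timed from the infusion, so they have no starting point for such a person. The nine-month visit is timed from surgery, so it could still take place.

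**The concern.** When a check that can stop treatment comes after allocation, its failures become a problem inside the randomised comparison. If they are kept in their assigned arm, an uninfused active-arm participant pulls the estimated effect towards zero. If they are removed, a small comparison loses people after allocation. Had the check come before allocation, neither would happen.

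The order also matters for who makes the decision. Acute kidney impairment is given no criterion in the text, so it calls for judgement. The only person stated to be blinded is the DXA technologist. The documents do not show that whoever judges the panel is unaware of the arm.

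At stake are the 9-month estimate that feeds the next trial's sample size, and the denominators for retention and for tolerance of the infusion, which are the primary feasibility measures.

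**Working it through.** **Inputs from Statistical Analysis.** Difference 0.02 and SD 0.02, so the standardised effect is d = 0.02 / 0.02 = 1.0. Two-sided alpha 0.05. 15 randomised and 10 completing per arm. **Assumed, because the documents do not give it:** the share failing the kidney check after allocation, taken as 1% to 10%. An uninfused active-arm participant is assumed to respond like a placebo participant.

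**1. The plan's own figure.** The plan states "A sample size of 10 per group achieves 80% power to detect a difference of -0.02", "with an estimated standard deviation of 0.02". A two-sample t-test with 10 per group and d = 1.0 has 56.2% power. A two-sample Wilcoxon test has about 51% to 52% by simulation. The stated 80% is matched only by a one-sample or paired test on 10 people (80.3% by t-test). That is a separate matter; the baseline used below is 56%, the power of the t-test that the plan names for bone change.

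**2. How likely is at least one failure?** With failure rate q and 30 randomised, P(at least 1) = 1 − (1 − q)^30.

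| q (assumed) | Among 30 | Among 15 in the active arm |
|---|---|---|
| 1% | 26% | 14% |
| 2% | 45% | 26% |
| 5% | 79% | 54% |
| 10% | 96% | 79% |

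Only the last column bears on dilution, because an uninfused placebo participant does not change the expected difference.

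**3. Dilution if they are kept as randomised.** With u uninfused among n analysed in the active arm, expected difference = 0.02 × (1 − u/n). The mixture also widens that arm: its expected sample variance is multiplied by 1 + u(n − u)/[n(n − 1)] when d = 1. For n = 10 this is 1.10 with u = 1 and 1.18 with u = 2. Power therefore has to be simulated from a mixed arm. Shrinking d alone and holding the SD fixed gives 48% and 40% for n = 10, which is too favourable.

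| Analysed per arm | u | Expected difference | t-test power (simulated for u = 1 or 2) |
|---|---|---|---|
| 10 | 0 | 0.020 | 56% |
| 10 | 1 | 0.018 | 46% |
| 10 | 2 | 0.016 | 36% |
| 15 | 0 | 0.020 | 75% |
| 15 | 1 | 0.0187 | 68% |
| 15 | 2 | 0.0173 | 61% |

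**4. Effect on the next trial's size.** Planning on 0.020, 0.018 or 0.016 with SD 0.02, 80% power and a two-sided t-test requires 17, 21 or 26 per arm.

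**5. Loss of numbers if they leave instead.** The allowance is 15 − 10 = 5 per arm. The probability that this cause alone takes more than 5 of 15 is 0.2% at q = 10%, and lower for smaller q. Such losses therefore come out of the allowance first and reduce the 10 completers only if other losses have already used it up.

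**The case against.** Several points on the other side are sound.

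- **Frequency is unknown.** The documents give no failure rate, and the text available has no eligibility section, so earlier kidney screening can be neither assumed nor excluded. At q = 1% the chance of two or more failures among 15 in the active arm is 1%; at 2% it is 3.5%. The lower rows of the dilution table may never occur.
- **The GFR may be taken earlier.** It is called a baseline value and could precede allocation. The rapid panel and the acute-impairment criterion still point to the infusion visit, so the order stands as a reading of the text.
- **The pilot is exploratory.** Bone change is a secondary analysis in Statistical Analysis (the Summary calls it primary), and non-infusion is part of the compliance that the Summary's second aim sets out to document. An as-randomised estimate that includes a few uninfused people is legitimate, and is informative for a later trial with the same check. This limits the importance of the point, but the plan still does not say that this is the estimate it will produce.

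Two stronger readings are tempting and are not supported. A reader might infer that treatment is withheld only in the zoledronic acid arm, so that exclusions are unbalanced and the comparison is biased. But everyone is tested, and the withholding sentence refers back to those participants. A pre-infusion result applied alike in both arms, without knowledge of assignment, costs numbers and need not bias. The wording is at most ambiguous. A reader might also subtract one or two people from the 10 completers in the active arm and quote 54% (9 against 10) or 51% (8 against 10). That ignores the five-per-arm allowance.

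**Conclusion.** The point holds at modest size. As written, allocation precedes the check that can stop the infusion, and no rule covers a participant who is randomised and then not infused. If one or two such people are in the active arm and are analysed there, the expected difference falls by 10% or 20% with 10 analysed per arm (t-test power down about 10 or 20 percentage points), and by 7% or 13% with 15 per arm (power down about 7 or 14 points). This rests on the plan's difference and SD, on a placebo-like response in the uninfused, and on an assumed failure rate that could be zero. Loss of numbers from this cause is minor, and bias between arms is not shown. The reason to act is that the remedy is cheap and makes it impossible for the infusion decision to depend on the arm.

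**What to change.** Release the assignment at the infusion visit, only after the panel result is known and the participant is confirmed for infusion. State that the check applies identically in both arms. State also that everyone randomised is followed to nine months and analysed in the assigned arm, including anyone not infused, and say how such a person counts towards retention and tolerance.

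This uses the same blood draw and leaves the kidney rule as it is. The cost is a short protocol change and less notice for preparing the infusion. The new order also removes withdrawals between allocation and the visit, but not losses after infusion, and it does not bring power to the stated 80%. If the present order has to stay, the statements on identical application, follow-up and analysis are still needed.

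### The Summary promises adverse-event documentation at every time point, but the nine-month visit has no adverse-event question, so events starting after the 2-month contact are not systematically asked about

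*Combined protocol and SAP*

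**What the plan says.** Specific Aim 2 appears in two forms. The Summary words it as "To evaluate the feasibility of this trial in those who have undergone sleeve gastrectomy surgery", and gives the means: "We will assess the feasibility of the intervention by documenting adverse events and compliance rates at each study time point". The Purpose section words it as "evaluate the safety and tolerance of zoledronic acid in populations who have undergone SG surgery".

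The Methods then describe the collection itself. At the infusion visit, "Adverse events including potential infusion reaction and other side effects will be recorded by study personnel at the time of infusion", and "a Clinical Research Center nurse will be present during the infusion and will monitor the patient for 15 minutes after the infusion". Afterwards participants are contacted "24-hours and 2-months following their infusion to collect and address any adverse events/reactions/concerns they may have". The tool is a REDCap self-report survey, or the adverse events form completed by staff if contact is by phone. Non-responders are tried up to 3 times.

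The next visit is introduced with "Nine months post-bariatric surgery, participants will have a follow-up visit". Its content is listed: weight, waist circumference, a blood draw for bone markers and metabolic proteins, three questionnaires (activity, knee, dietary calcium) and three function tests (grip, chair stands, gait speed). Adverse events are not in that list, nor in the description of the DXA and CT scans a month later.

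The Statistical Analysis section calls all analyses exploratory. It plans to report retention and a descriptive account of how each group tolerated the infusion.

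**The concern.** Adverse events are what the plan has for the safety and tolerance side of Aim 2. The Summary promises them at every time point, but the visit procedures carry that promise only as far as 2 months after infusion. Staff work from visit procedures. If they follow the nine-month list as written, nobody asks about the preceding months, in the treated or the placebo arm.

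The adverse-event record would then stop at 2 months while the bone outcomes run to nine months and beyond. This pilot is meant to inform a larger trial, and a blank late period could be taken for a period without events. The gap is wider for a participant who cannot be reached at 2 months, because the last question that person answered was at 24 hours or at the infusion itself.

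**Working it through.** **Step 1. Time points against procedures.** This is a comparison of text; the plan gives no figure to reproduce.

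| Time point | Adverse-event collection described? |
|---|---|
| Infusion | Yes: recorded by staff, with 15 minutes of nurse monitoring |
| 24 hours after infusion | Yes: survey link, or form by phone |
| 2 months after infusion | Yes: survey link, or form by phone |
| Nine-month visit | No: other measurements are itemised, no adverse-event item |

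That is 3 of 4. The scan appointment one month after the nine-month visit has no adverse-event item either.

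**Step 2. Length of the unasked period.** The nine-month visit is timed from surgery and the adverse-event contacts are timed from infusion. The document does not give the interval between surgery and infusion. Let L be the months by which infusion precedes surgery (negative if it follows).

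- Infusion to nine-month visit = 9 + L
- Last adverse-event contact to nine-month visit = (9 + L) − 2 = 7 + L

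| L (assumed) | Infusion to visit | Unasked period | Share |
|---|---|---|---|
| 2 | 11 months | 9 months | 9/11 = 82% |
| 1 | 10 months | 8 months | 8/10 = 80% |
| 0 | 9 months | 7 months | 7/9 = 78% |
| −1 | 8 months | 6 months | 6/8 = 75% |
| −2 | 7 months | 5 months | 5/7 = 71% |

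For a participant who misses the 2-month contact, the unasked period starts at 24 hours and is close to the full 9 + L months.

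**Step 3. Denominators, once a nine-month form exists.** The plan enrols 15 per arm and aims for 10 completers per arm. At that goal, 30 − 20 = 10 participants (one third) would have no nine-month form. Suppose late events were divided by all 15 in an arm when only 10 had been asked, and all 15 had been infused. The reported proportion would be 10/15 = 0.67 of the proportion among those asked. Those without a form would in effect be counted as free of late events. The denominator therefore has to change with the period.

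**Step 4. Burden.** One extra form per participant at a visit that already exists: 2 × 10 = 20 forms at the completion goal, and at most 2 × 15 = 30.

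**The case against.** The best reply is that the Summary already covers the nine-month visit, and the Methods simply do not repeat it. The Methods are plainly not exhaustive. Vitamin D is dosed by a serum level that no described blood draw names, and the compliance rates promised in the same sentence of the Summary have no procedure at any visit. Silence in the nine-month list is therefore weak evidence that staff would not ask. This stands in part: it shows the intent. It does not supply a procedure, and the survey and form are mentioned only with the 24-hour and 2-month contacts.

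A second reply is that only short-term tolerance was intended, which is how the Statistical Analysis section reads. Collection to 2 months fits that outcome. But then the Summary's promise is too wide and the Purpose wording too broad, so some text still has to change.

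Three stronger readings are tempting and are not supported:

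- A reader might infer a deliberate cut-off at 2 months. No section states one.
- A reader might infer that the plan would lead to a claim of renal safety, since the only kidney measurements described come before infusion ("all participants will have a baseline glomerular filtration rate (GFR) measured prior to infusion to ensure they have adequate kidney function"). That check decides whether a participant may be dosed. No section plans a renal conclusion or a safety conclusion for the whole follow-up, so the overclaim is hypothetical.
- A reader might infer that most adverse events would be lost. The shares in the working are shares of time. The document gives no event rates, so the fraction of events that fall in the gap cannot be calculated.

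**Conclusion.** The point holds as a mismatch between what is promised and what is scheduled. Adverse-event collection is described at 3 of the 4 time points from infusion to the nine-month visit. Events that start after the 2-month contact, or after 24 hours in those who miss it, are not systematically asked about in either arm. A participant may still volunteer an event, and staff may still ask on the strength of the Summary, so this is a gap in procedure and not proof that late events will go unrecorded.

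Its length cannot be fixed from the document. About 7 months rests on the assumption that infusion is near surgery, and 5 to 9 months on an assumed interval of up to 2 months either way. The analyses of bone outcomes are not affected. The change is worth making because it alters what data are collected for a stated aim, at very little cost.

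**What to change.** 1. In the Methods, add the existing adverse events form to the nine-month visit in both arms. Ask about events since the last completed contact, with start dates. This also recovers events in those who missed the 2-month contact.
2. In the Statistical Analysis section, report events by arm and by period. Use all infused participants for events at infusion; those who completed the 24-hour or 2-month contact for events up to each; and those who completed the nine-month form for later events. State the number of missing forms in each period.
3. Word the conclusions for Aim 2 as a description of reported events and tolerance, in line with the Statistical Analysis section.

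The cost is one line in the Methods, a short reporting paragraph and 20 to 30 forms. There are two downsides. Recall over several months is weaker than at a 2-month contact. Events due to the surgery will be recorded in both arms, so late events should be read by comparing arms and not as counts in the treated arm alone.
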